## **6.5 POOLING OF CENTRES**

This section is not applicable because this is the safety surveillance PASS study and no statistical model is involved in the analysis.

## **6.6 HANDLING OF MISSING DATA AND OUTLIERS**

No missing data analysis is planned for this study. Missing values will be considered as missing, no imputation will be done for the analysis purpose.

No imputation is planned for missing AE data except for missing or incomplete AE onset dates which will be imputed according to BI standards  (i.e. “Handling of missing and incomplete AE dates”) as below.

Step 1: For each missing / incomplete AE onset date, an interval (INT\_START, INT\_END) is defined. The true unknown analysis start date of AE is assumed to be within the interval.

Scenario of AE onset date	INT_START	INT_END
Completely missing AE onset date	Min (AE end date, Date of informed consent)	Min (AE end date, Date of last visit)

Scenario of AE onset date	INT_START	INT_END
Only year of AE onset date is non-missing	Min (AE end date, 01 JAN of the reported year)	Min (AE end date, 31 DEC of the reported year)
Only year and month of AE onset date is non-missing	Min (AE end date, 01 of the reported month)	Min (AE end date, Last date of the reported month)

Note: Completely missing AE end date will not be considered in this derivation step.

Partially missing AE end date will be temporarily assigned the largest possible date in the observed year or month in the derivation step.

Step 2: Derive an imputed AE onset date based on the interval from step 1.

Scenarios	TESS/ Non-TESS	Imputed AE onset date
1. Date of first drug administration is within the interval [INT_START, INT_END]	TESS	Date of first drug administration
2. Date of first drug administration is before INT_START*	TESS	INT_START from step 1
3. Date of first drug administration is after INT_END or missing	Non-TESS	INT_END from step 1

TESS- Treatment emergent AE

\*Note: If INT\_START is after the date of the last drug administration plus residual effect period, then the AE is non-TESS.

Step 3: The AE onset date imputation flag(s) are set according to the level of imputation performed and the standard CDISC rules for imputation or the legacy data imputation rules.

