10.4 DATA SOURCES

This active surveillance is based on existing and newly collected data at selected centers where IPF patients are regularly treated.

Data of the individual patients will be gathered using electronic data capture (EDC) system. The medical records of Group A and B patients will be used to collect the data of covariates as described in [section 10.3.3](#) and all ADRs and SAEs occurring during the duration of the treatment/ 52 weeks, whichever is earlier. This data will be entered into eCRF and reported via NIS AE form as per [section 12.2](#). Group B and C patients will be followed-up according to clinical practice for at least 52 weeks/discontinuation (whichever is earlier) from the start of the treatment, at regular intervals (i.e. approximately every 4 weeks for the first 3 visits and every 12 weeks thereafter till week 52). After the completion of medical examination and observation at the suggested time points, investigator needs to enter data of the registered patients (all ADRs and SAEs) in the EDC system and report via NIS AE form as per [section 12.2](#). Additionally information on certain covariates will be collected at subsequent visits as described in the [section 10.3.3](#). For patients treated with Pirfenidone, only baseline characteristics will be recorded in EDC and these patients will not be followed.

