## **6 GENERAL ANALYSIS DEFINITIONS**

### **6.1 TREATMENT**

This active surveillance will include 200 IPF patients treated with nintedanib per the Indian label. They are classified into following groups:

Group B:	Patients who started treatment with nintedanib after 23rd January, 2017 and are continuing the drug at the time of participation in the active surveillance.
Group C:	Patients who have been newly prescribed nintedanib at the time of participation in the active surveillance.

In addition 200 IPF patients treated with pirfenidone will also be enrolled. They are classified into following groups:

Group II:	Patients who started treatment with pirfenidone after the 23rd January, 2017 and are continuing the drug at the time of participation in the active surveillance.
Group III:	Patients who have been newly prescribed pirfenidone at the time of participation in the active surveillance.

The medical records at the selected sites will be screened to enroll Group B patients in a retrospective manner till the date of start of their participation in this active surveillance program and prospectively thereafter. Group C patients will be enrolled prospectively. The first patient enrolled at a given site should be in the nintedanib group. Once a patient is enrolled into the nintedanib group, the site team is suggested to enroll the next eligible patient, who has initiated or will be initiating pirfenidone at the same site in the pirfenidone group.

As this is an active surveillance of patients prescribed nintedanib in the real world, no specific treatment is mandated or withheld from the patients. The choice of maintenance treatment for IPF must be according to regular medical practice and at the discretion of the physician. As for any active surveillance study, the assignment of the patient to nintedanib

or any other treatment falls within current practice and prior to the decision to talk to the patient about the study, so that the decision to prescribe nintedanib is clearly separated from the decision to include the patient in this active surveillance. The decision of treatment, including the intended duration of treatment, is at the discretion of the physician providing care for the patient.

Patients who have taken at least one dose of nintedanib will be included in the safety analysis.

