### **7.8.1 Adverse events**

Adverse events will be collected at the time points or visits specified in flowchart presented in the CTP. The medical records of patients belonging to Group B will be evaluated to see if any ADRs and SAEs have occurred in the nintedanib treated arm during the duration of the treatment before participation in the active surveillance. Group B and Group C patients will be followed up according to clinical practice as per the suggested visit. At each visit, all ADRs associated with nintedanib and SAEs will be recorded and reported.

No adverse events of special interest (AESI) have been defined for this active surveillance.

AEs will be coded using the current version of the Medical Dictionary for Regulatory Activities (MedDRA) version 20.0 or higher and will be based on the concept of treatment emergent AEs. All AEs occurring between first intake of nintedanib prescribed and up to 52 weeks or discontinuation of the drug (or the final contact with the patient for the last regular observation/end of the study) will be considered ‘treatment emergent’. Adverse event summaries will summarize only treatment emergent adverse events (TEAEs), which are defined as AEs not present prior to the nintedanib prescribed.

An AE is considered to be an ADR if either the physician who has reported the AE or the sponsor assesses its causal relationship (at least a reasonable possibility of a causal relationship) between event and drug checked as 'Yes'.

TEAEs will be categorized into one or more of the following categories depending on the type of events reported:

- All TEAEs
- All TEAEs by severity
- All SAEs
- Non-Serious TEAEs
- TEAEs leading to death
- All treatment related TEAEs
- All treatment related SAEs
- All treatment related Non-Serious TEAEs
- All treatment related TEAEs leading to death
- TEAEs leading to Treatment discontinuation
- TEAEs leading to dose reduction
- TEAEs leading to dose interruption

The frequency and incidence rate of AEs/SAEs and ADRs will be tabulated by system organ class and preferred term.

Multiple overlapping or adjacent AE occurrence of same AE are collapsed into one AE event according to BI standard [\(7\)](#).

Two AE are considered to be time-overlapping if the start date of the second, later occurrence is earlier or equal to the end date of the first occurrence.

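### For a completely missing AE onset, SAP 6.6 starts the interval at informed consent, so Group B chart-review events get their latest possible date and the ADR and SAE incidence rates are slightly understated

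*SAP*

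**What the plan says.** SAP 6.6 imputes missing or incomplete AE onset dates in two steps. Step 1 builds an interval, on the premise that "The true unknown analysis start date of AE is assumed to be within the interval". For a completely missing onset the interval starts at "Min (AE end date, Date of informed consent" and ends at the earlier of the AE end date and the last visit. A wholly missing end date is ignored. For a year-only onset the start is "Min (AE end date, 01 JAN of the reported year", with no reference to consent. Step 2 then compares the interval with first intake:

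- First intake inside the interval (scenario 1): the onset becomes first intake.
- "Date of first drug administration is before INT_START" (scenario 2): the event is treatment-emergent and the onset becomes INT_START.
- First intake after the interval, or missing (scenario 3): the event is not treatment-emergent.

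SAP 6.1 defines Group B as "Patients who started treatment with nintedanib after 23rd January, 2017 and are continuing the drug at the time of participation in the active surveillance". SAP 7.8.1 adds that "The medical records of patients belonging to Group B will be evaluated to see if any ADRs and SAEs have occurred" before participation. SAP 6.6 has no separate rule for this group.

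On the window, SAP 7.8.1 counts events as treatment-emergent "up to 52 weeks or discontinuation of the drug (or the final contact with the patient for the last regular observation/end of the study". Protocol 10.4 has the Group A and B record review collect "all ADRs and SAEs occurring during the duration of the treatment/ 52 weeks, whichever is earlier".

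**The concern.** An interval that starts at consent suits patients who consent before their first dose. In Group B the order is reversed. An event already in the chart at consent began before consent, so an interval that opens at consent cannot contain its onset, contrary to the rule's own premise. If the event resolved before consent, both ends of the interval equal the AE end date and the interval is a single day.

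The error runs in one direction. SAP 7.4 counts time at risk from treatment start to the first onset of the event and divides the number of patients with the event by the total. A late onset enlarges the denominator and lowers the rate. Both primary outcomes, ADR and SAE incidence, are reported this way, and understating risk is the unwelcome direction for safety surveillance.

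The percentage of patients with an event is untouched unless an imputed onset falls after week 52 and the event is then removed.

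**Working it through.** The plan states no rate for this point, so there is no figure to reproduce. The check applies the rule to dates and then sizes the effect under assumptions.

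**Rule applied to dates** (day = imputed onset − first intake + 1)

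Group B patient with first intake 2 Oct 2017 and consent 3 Sep 2018 (week 48):

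| Recorded onset | Event end | Imputed onset | Day |
|---|---|---|---|
| Year 2017 only | ongoing | 2 Oct 2017 (scenario 1) | 1 |
| Year 2018 only | ongoing | 1 Jan 2018 (scenario 2) | 92 |
| None | ongoing | 3 Sep 2018 (scenario 2) | 337 |
| None | 1 Mar 2018 | 1 Mar 2018 (scenario 2) | 151 |

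With no date at all, the same ongoing event lands 336 days later than if the record says only 2017. A Group C patient who consented before first intake would get day 1 for an undated ongoing event.

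**Beyond week 52.** With first intake 1 Jun 2017, consent 1 Sep 2018 and neither onset nor end date, the imputed onset is day 458. Week 52 ends on day 364 (30 May 2018). Step 2 still labels the event treatment-emergent. Its exception for onsets after last drug plus the residual effect period does not apply, because Group B patients are still on drug at participation. Such timing is possible: all but 6 subjects are on protocol version 5.0, dated 1 Aug 2018, which is 555 days after 23 Jan 2017. A Group B patient enrolled under it who started before about August 2017 consents after week 52.

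**Pooled ADR rate**

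From the documents: 200 nintedanib patients, 52 weeks (364 days), rate = 100 × patients with event ÷ patient-years.

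Assumed: 40% have an ADR; mean true onset is 56 days (exponential, truncated at 364); resolved events last 28 days; half of the undated events are ongoing; Group B is 25-50% of the treated set; 5-10% of its pre-consent onsets are wholly undated after queries.

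- No missing dates: (120 × 364 + 80 × 56) ÷ 365.25 = 131.85 patient-years; 100 × 80 ÷ 131.85 = 60.7.
- Group B 50%, 10% undated: 100 × 0.4 × 0.1 = 4 patients, of whom 2 are ongoing.
- Consent at week 39 (day 273): true onsets before that day average about 54, so added time ≈ 2 × (273 − 54) + 2 × 27 = 492 days. Rate = 100 × 80 ÷ (48,652 ÷ 365.25) ≈ 60.1, or −1.0%.
- Consent at week 60 (day 420), events kept: added time ≈ 2 × (420 − 56) + 2 × 27 = 782 days. Rate ≈ 59.7, or −1.6%.
- Consent at week 60, the two late events dropped and those patients counted to day 364: 78 events, added time ≈ 2 × 308 + 2 × 27 = 670 days. Rate ≈ 58.3, or −3.8%.

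The full calculation on a daily grid gives, per 100 patient-years:

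| Group B share, undated | Week 13 | Week 26 | Week 39 | Week 60 kept | Week 60 dropped |
|---|---|---|---|---|---|
| 50%, 10% | 60.51 | 60.29 | 60.07 | 59.71 | 58.35 |
| 25%, 5% | 60.64 | 60.58 | 60.52 | 60.43 | 60.09 |

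If every undated event is ongoing (50%, 10%), the change is −1.8% at week 39, −2.9% at week 60 kept and −7.4% at week 60 dropped. The last figure stacks several extremes.

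**Single terms.** For a term with 10 events in 184 patient-years, one onset placed 0.5 years late gives 10 ÷ 184.5, a fall of 0.3%. Dropping one event costs about 10% of the rate with 10 events and about 25% with 4.

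**The case against.** The strongest reply is that this hardly matters. With 80 events in 131.85 patient-years, the exact interval from SAP 7.4 is about 48.1 to 75.5, roughly −21% to +24% around the estimate. The analysis is descriptive, with no comparator for safety, so no conclusion turns on a shift of about 1%. SAP 7.8.1 expects complete onset dates and sends gaps to data management first. A chart entry will often supply at least a year or month, and partial dates do not use consent. The 5-10% residual has no support in the documents. All of this stands and keeps the impact low. It does not make the rule right for Group B, and a one-directional error is not part of the sampling uncertainty that the interval describes.

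Three further points stand in part:

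- The pooled rate is a simplification. The planned tables are by system organ class and preferred term, and for an any-ADR rate an undated event matters only if it changes the patient's first onset.
- Anchoring at first intake errs the other way. With 50% Group B, 10% undated and consent at week 13, the present rule is off by 60.51 − 60.68 = −0.17 and the repair by 60.81 − 60.68 = +0.13. The gain comes with later consent.
- The week-52 question is separable, since it concerns any onset imputed past the window. It is raised here because the consent anchor creates such onsets.

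That the rule is the sponsor's standard, which Protocol 10.7.1 invokes, explains where it comes from but does not make it fit patients who consent after dosing.

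**Conclusion.** The concern holds: the rule is wrong as written for Group B, with low impact. That the imputed onset is the latest possible one, and that the rates are lowered, follows from the SAP text alone. The exception is an event that ended on or before the day of first intake.

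The size rests on assumptions: about 0.1-1.0% with consent at weeks 13-39, and 0.4-1.6% at week 60 if the events stay treatment-emergent. The larger falls need events to be dropped after week 52. The documents do not settle that: Step 2 keeps them, while SAP 7.8.1 and Protocol 10.4 point to a 52-week limit and 7.8.1 also mentions final contact or end of study. The Group B share, the consent timing and the number of wholly undated onsets are not given, so these figures are illustrative.

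**What to change.** In the row of SAP 6.6 Step 1 for completely missing onsets, add: for events identified in the pre-consent record review of a patient whose consent follows first intake, INT_START = Min(AE end date, date of informed consent, date of first nintedanib intake). Scenario 1 then imputes first intake, and events that ended before first intake remain non-treatment-emergent under scenario 3. Keep the present row for events first arising after consent.

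Reconcile SAP 6.6 Step 2, SAP 7.8.1 and Protocol 10.4 for onsets after week 52, and state that treatment-emergent status follows the reconciled 7.8.1 window. Report the number of imputed onsets by Group; Step 3 already sets the imputation flags. If that number is not trivial, show the rates with onset at first intake and at the earlier of end date and consent. The two bracket the truth for record-review events that began on treatment.

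The cost is one table line, one sentence on the window, and a flag separating record-review from prospective events. Whether the CRF already captures that flag cannot be seen from the documents. First intake is a convention, not the true date: under the same assumptions the rates err high by about 0.1-0.5% (60.81 to 60.96 against 60.68 in the 50%, 10% case), and by more if more dates are missing. For safety surveillance that is the conservative direction.

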12.2 ADVERSE EVENT AND SERIOUS ADVERSE EVENT COLLECTION AND REPORTING

The investigator shall maintain and keep detailed records of all AEs in their patient files.

Collection and Reporting of AEs

The design of this active surveillance is of non-interventional nature and will be conducted within the conditions of the approved marketing authorisation. Sufficient data from controlled interventional trials are available to support the evidence on the safety and efficacy of the studied BI drug. For this reason the following AE collection and reporting requirements have been defined.

The following information must be collected for Group A,B and C patients from the date of initiation of nintedanib until individual patient's end of study:

- All ADRs associated with nintedanib
- All SAEs in patients exposed to nintedanib

All ADRs and SAEs including those persisting after study completion must be followed up until they are resolved, have been sufficiently characterized, or no further information can be obtained.

The investigator carefully assesses whether an AE constitutes an ADR using the information below.

Causal relationship of adverse event:

The definition of an adverse reaction implies at least a reasonable possibility of a causal relationship between a suspected medicinal product and an adverse event. An adverse reaction, in contrast to an adverse event, is characterised by the fact that a causal relationship between a medicinal product and an occurrence is suspected.

Medical judgment should be used to determine the relationship, considering all relevant factors, including pattern of reaction, temporal relationship, de-challenge or re-challenge, confounding factors such as concomitant medication, concomitant diseases and relevant history.

Arguments that may suggest **a reasonable causal relationship** could be:

- The event is **consistent with the known pharmacology** of the drug
- The event is known to be caused by or **attributed to the drug class**.
- A **plausible time to onset of the event** relative to the time of drug exposure.
- Evidence that the **event is reproducible** when the drug is re-introduced
- **No medically sound alternative etiologies** that could explain the event (e.g. pre-existing or concomitant diseases, or co-medications).
- The event is typically **drug-related and infrequent in the general population** not exposed to drugs (e.g. Stevens-Johnson syndrome).

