### **6.3 PATIENT SET ANALYSED**

➤ **Screened Set:**

Screened Set includes all patients who sign the ICF by either voluntarily or patient's legally authorized representative.

➤ **Entered Set:**

Entered Set includes patients in screened set who met the eligibility criteria.

➤ **Treated Set:**

Treated Set includes patients in entered set who have taken at least one dose of nintedanib.

Analysis for all primary and secondary outcomes will be done on treated set.

The following table defines the patient set is to be used for planned analysis.

Table 6.3: 1 Patient sets analyzed

Class of endpoints/outcomes	Patient set		
	Screened Set	Entered Set	Treated Set
Primary and key secondary outcomes (Safety)	-	-	X
(Other) Secondary and further outcomes	-	-	X
Demographic/baseline outcomes	-	X	-

Note: No key secondary and further outcomes mentioned in CTP.

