## **7 PLANNED ANALYSIS**

- All study data will be included in individual patient study data listings. In general, all data will be listed by therapy prescribed and by visit (if applicable). The basic data like demographic and baseline characteristics, patient disposition and patient analysis set will be listed and also summarized by therapy prescribed, by Group. All summary tables will represent descriptive statistics for the parameters being analyzed, wherever applicable.
- Numeric presentations:
  - Non-integer numerical data should be presented with decimal point.
  - If the non-formatted data (e.g. which is received from the clinical database) is inconsistently presented, a decision on how to present the final data will be made on a case-by-case basis.
  - When rounding is required, number 4 or below will be rounded down and number 5 or above will be rounded up.
  - When deriving new variable(s) based on raw data, no rounding will be performed at intermediate calculation. Rounding will only be performed when displaying data.
  - Descriptive analysis for continuous data will include number of non-missing observations (n), mean, standard deviation (SD), median, minimum, maximum, Q1, and Q3. Means, medians, Q1 and Q3 will be rounded to 1 decimal place more than the original data. Standard deviation will be rounded to 2 decimals place more than the original data. Minimum and maximum will be displayed with the same decimal precision as the original data.
  - For categorical data, frequency and percentage with corresponding 95% confidence interval will be presented wherever applicable. Confidence interval and percentages will be rounded to 1 decimal place. Percentages equal to 100 will be output as '100'. The counts and percentages equal to 0 will be represented as '0' only.
- Missing data will not be imputed but will be analyzed as missing.

- Baseline assessments are the assessments taken at the Visit 1 for all patients. If there are multiple assessments collected on the same scheduled time, the average of these assessments will be used.
- The change from baseline is defined as the post-baseline value minus the baseline value.
- Text column should be left justified.
- All the data analysis will be done using SAS® version 9.4.

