### **Derivation of Time at Risk in Patients-years for a specific AE**

- Patients with specific AE:

Time at risk (AE) in days = (Start date of first specific AE - Treatment start date) +1

- Patients without specific AE:

Time at risk (AE) in days = Overall time at risk = (End date of time at risk - Treatment start date) +1

Total AE-specific time at risk is derived as below:

Time at risk (AE) [years] = Sum of time at risk [days] across all patients / 365.25

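### The SAP's onset-date rule makes an incompletely dated event non-treatment-emergent when the first-dose date is missing, even in patients known to have taken nintedanib

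*SAP*

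**What the plan says.** SAP 6.6 builds an interval for the unknown onset of an event and compares it with the date of first drug administration. Scenario 3 of Step 2, "Date of first drug administration is after INT_END or missing", gives the label Non-TESS and sets the onset to the end of the interval.

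Only onset dates are imputed: "No imputation is planned for missing AE data except for missing or incomplete AE onset dates". Everything else follows the general rule "Missing values will be considered as missing, no imputation will be done for the analysis purpose", and SAP 7 repeats it: "Missing data will not be imputed but will be analyzed as missing". No rule covers a missing or partial treatment start date.

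Four other places determine what follows:

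- SAP 7.8.1 limits the tables: "Adverse event summaries will summarize only treatment emergent adverse events (TEAEs".
- SAP 6.3 defines the set used for both primary outcomes by intake, not by a known date: "Treated Set includes patients in entered set who have taken at least one dose of nintedanib".
- Protocol 12.2 has ADRs and SAEs collected "from the date of initiation of nintedanib until individual" patient's end of study.
- SAP 7.4 needs the start date for person-time: "Time at risk (AE) in days = (Start date of first specific AE - Treatment start date) +1". The formula for patients without the event subtracts the same date.

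**The concern.** Scenario 3 puts two different situations under one label: an event that ends before the first dose, and an event in a patient whose first-dose date is not recorded. The default is reasonable where a missing first-dose date means the patient was never dosed. In this study it does not mean that. Every Treated Set patient took the drug, Group B is defined as having started after 23 January 2017 and still being on treatment at enrolment, and event collection begins at initiation. An ADR is also, by definition, judged related to nintedanib. Labelling such an event as not treatment-emergent contradicts the study's own definitions.

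The case can arise because Group B data before enrolment come from medical records. Both primary outcomes, the incidence of ADRs and of SAEs, are at stake. Each is reported as a percentage and as a rate per 100 patient-years, and the two measures are affected differently.

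**Working it through.** The plan gives no figure that depends on this rule, and the 200 nintedanib patients are a regulatory request without a formula, so there is nothing to reproduce first. The check has two parts.

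**1. The rule applied to one event.** Invented Group B case: onset recorded only as March 2018, event ended 20 March 2018.

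- Interval start = min(20 March, 1 March) = 1 March 2018.
- Interval end = min(20 March, 31 March) = 20 March 2018.
- Time at risk = onset − treatment start + 1 (SAP 7.4).

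| First-dose date | Class | Imputed onset | Days at risk |
|---|---|---|---|
| 10 Feb 2018 | TESS | 1 Mar 2018 | 20 |
| 10 Mar 2018 | TESS | 10 Mar 2018 | 1 |
| missing | Non-TESS | 20 Mar 2018 | not computable |

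If the start were known only as February 2018, either end of that month gives TESS, with 29 days (from 1 February) or 2 days (from 28 February). If it were set to 24 January 2017, the first day after the eligibility date, the result is 402 days, which exceeds the 52 × 7 = 364 days of the treatment-emergent window.

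**2. Effect on the summaries.** Every input here is assumed except N = 200. Let p be the true share with an event (30% or 60%), m the share with a missing first-dose date (2%, 5%, 10%), and q the share of affected patients with an event whose event is incompletely dated (100% or 25%). Mean time at risk is 0.25 years with an event and 1 year without. The missing dates are spread evenly over patients with and without events, and fully dated events are still counted.

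- Patients counted = 200p(1 − mq); percentage = that number / 200.
- Person-years counted = (1 − m) × [200p × 0.25 + 200(1 − p) × 1].
- Rate = 100 × patients counted / person-years counted.

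With nothing missing:

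- p = 30%: 60 patients, 60 × 0.25 + 140 = 155 person-years, rate 38.7 (exact 95% CI 29.5 to 49.8).
- p = 60%: 120 patients, 120 × 0.25 + 80 = 110 person-years, rate 109.1 (90.4 to 130.4).

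Example for p = 30%, m = 5%:

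- Person-years = 155 × 0.95 = 147.25.
- q = 100%: 60 × 0.95 = 57 patients, 28.5%, rate 100 × 57 / 147.25 = 38.7.
- q = 25%: 60 × (1 − 0.0125) = 59.25 patients, 29.63%, rate 100 × 59.25 / 147.25 = 40.2.

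| p | m | Person-years lost | %, q = 100% | Rate, q = 100% | %, q = 25% | Rate, q = 25% |
|---|---|---|---|---|---|---|
| 30% | 2% | 3.1 | 29.4 | 38.7 | 29.85 | 39.3 |
| 30% | 5% | 7.8 | 28.5 | 38.7 | 29.63 | 40.2 |
| 30% | 10% | 15.5 | 27.0 | 38.7 | 29.25 | 41.9 |
| 60% | 2% | 2.2 | 58.8 | 109.1 | 59.70 | 110.8 |
| 60% | 5% | 5.5 | 57.0 | 109.1 | 59.25 | 113.4 |
| 60% | 10% | 11.0 | 54.0 | 109.1 | 58.50 | 118.2 |

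The percentage always falls. The rate stays put when numerator and person-time drop together, and rises when fully dated events stay in the numerator without their person-time. Every shifted rate lies inside the confidence interval of the complete-data rate.

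**The case against.** The strongest reply is that the case is rare. An event is lost only if its onset is incomplete and the first-dose date is missing as well, and the design leans on that date throughout. Eligibility requires a start after 23 January 2017, visits and the 52-week limit run from treatment start, and exposure runs from initiation. Group B patients have consented, are still on the drug and are followed prospectively, so a site can ask. The mandatory registration items in protocol 10.2.2.3 do not list the nintedanib start date, but that does not show it goes uncollected: the amendment log refers to a drug-administration item in the flowchart, and the public text shows neither the flowchart nor the CRF. SAP 7.8.1 also sends missing onset dates to data management before any imputation, and the rule follows a company standard that may say more.

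Most of this stands, and it limits the size. It does not remove the defect. The query step is written for onset dates and does not mention first-dose dates. The SAP writes out the rule it will apply, and that text has no exception for treated patients. Person-time is also undefined for a patient whose events are all fully dated, because the formulas still need the start date.

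**Conclusion.** The point holds, as a minor one. As written, the rule misclassifies an incompletely dated event in a treated patient with no first-dose date. It biases the percentage down and leaves that patient's person-time undefined. How often this happens cannot be taken from the documents. The table in the working shows only how the error behaves under assumed inputs, and the true effect is probably small.

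A reader might infer more than the text supports:

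- **That chart-based patients lose all their events.** Scenario 3 acts only on events with a missing or incomplete onset, and even these remain in the individual listings.
- **That the bias runs one way.** It does for the percentage. The rate is unchanged or higher under the assumptions above, which include an even spread of missing dates.
- **That a definite share of the 200 patients is affected.** Neither the size of Group B nor the frequency of missing dates is given.
- **That a partial first-dose date counts as missing.** The SAP does not say how a partial start date is treated, so this would be an assumption.

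**What to change.** In SAP 6.6:

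- Limit the missing-date branch of scenario 3 to patients with no recorded nintedanib intake.
- For Treated Set patients with a missing or partial first-dose date, classify recorded ADRs and SAEs as treatment-emergent unless the known date parts place them outside the treatment window.
- Where the start date stays partial, impute it only within its known month or year and flag it. Show the primary rates with the earliest possible start, with the latest possible start, and without these patients.
- Where no part of the date is known, keep the event in the percentages and leave the patient out of the rates, both numerator and person-time.
- Do not use 23 January 2017 as a default start. As the test case shows, it can put an event outside the 52-week window and inflate person-time.

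In SAP 7.8.1, extend the query to data management to first-dose dates. This should settle most cases before any rule is needed.

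The cost is a few sentences, one derivation flag and a small sensitivity table. The only new data work is the query.
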